### 5.2 PARTICIPANT EXCLUSION CRITERIA

A potential participant who meets any of the following criteria will be excluded from participation in this study:

- DSM-IV diagnosis of alcohol or substance abuse (other than nicotine) within the last month or a DSM-IV diagnosis of alcohol or substance dependence (other than nicotine) within the last 3 months
- Positive urine test of cannabis, cocaine, amphetamine, barbiturates, opiates
- Current treatment (within 4 weeks) with psychotropic agents including benzodiazepines that are taken on a daily basis (limit prn use to greater than 48 hours before participating in study session)
- Medical or neurological illness (unstable cardiac disease, AIDS, malignancy, liver or renal impairment) or treatment for a medical disorder that could interfere with study participation
- History of traumatic brain injury that required subsequent cognitive rehabilitation, or cause cognitive sequelae
- A difference greater than 20% in AHRS scores between the 3rd and 4th screening visits
- Prior brain surgery
- Any brain devices/implants, including cochlear implants and aneurysm clips
- Co-morbid neurological condition (e.g. seizure disorder, brain tumor)
- Non English speakers
- Female participants who are pregnant, nursing, or unwilling to use an adequate method of contraception during study participation for those of child bearing potential
- Anything that, in the opinion of the investigator, would place the participant at increased risk or preclude the participant's likelihood of completing all components of the study

### 5.3 STRATEGIES FOR RECRUITMENT AND RETENTION

We intend to recruit 40 patients with schizophrenia or schizoaffective disorder and persistent auditory hallucinations, despite optimized antipsychotic medication treatment for at least 1 month. We will do this through both the UNC Hospital as well as the NCPRC Raleigh outpatient site, in coordination with providers at both locations. Additionally, we will also be contacting local ACT teams to recruit patients as well as potentially a small number from other community mental health providers. We estimate that approximately 15 subjects will be enrolled at the UNC-CH location, approximately 15 subjects will be enrolled at the Raleigh site, and approximately 10 subjects will be enrolled through ACT teams, for a total of 40 participants. Providers will be informed of the inclusion and exclusion criteria and will be asked to discuss the study with their patients at their next appointment or home visit in the case of the ACT team. Providers will include the medical teams treating patients at either of the two locations (Chapel Hill or Raleigh). Providers will identify patients they believe to be appropriate for this study based on the information we will provide them about the study. Providers will ask patients whether they are willing to be contacted by the research team regarding participation. Providers will be asked to avoid unnecessary medication changes leading up to and over the course of the study.

Our retention strategy includes monetary compensation for the time and effort required to participate in the study. The participant will receive a payment at each session of the study. The research staff will also give each participant a reminder call for the initial screening session, each follow up screening session, the first day of stimulation, and each maintenance session. Each research staff member will be easily available for the participants to contact via email or phone. The inclusion criteria state that each participant must be able to understand all risks and benefits associated with this study. We will be asking each participant to answer questions about the consent form to verify that the study process and the duration of participation are completely understood by all participants. We will aim to have a specific research team member assigned to complete all sessions with the same

participant. However we will not require the same researcher to be present during stimulation sessions 2 through 4. The study team will work hard at forming a professional relationship with the participants so they feel comfortable and willing to discuss what may be sensitive information. Retention will be quantified by participant attendance at each scheduled session (the data from each session will be scored and documented the day of the session). Participants will no longer be eligible to continue the study if they miss 2 consecutive stimulation sessions during the initial week of stimulation, if they miss 2 consecutive weeks of stimulation during the maintenance sessions, or if they miss more than 2 non-consecutive sessions during the course of the study. While we will ask each participant to complete an sMRI visit, it is not necessary for this visit to occur. If the participant does not want to complete the sMRI visit, the participant will be eligible to continue the remainder of the study.

## 5.4 PARTICIPANT WITHDRAWAL OR TERMINATION

### 5.4.1 REASONS FOR WITHDRAWAL OR TERMINATION

A study participant will be discontinued from further participation if:

- The participant has missed more than 2 non-consecutive stimulation sessions
- The participant has missed 2 consecutive stimulation sessions during the initial week of stimulation
- The participant has missed 2 consecutive weeks of stimulation during the maintenance sessions
- Any clinical adverse event (AE), laboratory abnormality, intercurrent illness or other medical condition, or situation occurs such that continued participation in the study would not be in the best interest of the participant.
- The participant meets any exclusion criteria (either newly developed or not previously recognized)
- A participant wishes to withdraw from further participation for any reason

### 5.4.2 HANDLING OF PARTICIPANT WITHDRAWALS OR TERMINATION

We will collect safety data on any participant discontinued because of an AE or SAE. In any case, every effort will be made to undertake protocol-specified safety follow-up procedures. If voluntary withdrawal occurs, the participant will be asked to continue scheduled evaluations and complete an end-of-study evaluation. If an AE has been reported, researchers will help the participant seek the medical care they need and a follow up will be performed by the PI or Co-I.

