#### **Day 5 of Stimulation (Visit 9)**

The participant will be asked to decide if they would like to complete the clinical assessments over the phone or in person. If they prefer the phone/webex, the participant will be contacted before coming into the lab and the AHRS (*Attachment 3*) and PANSS (*Attachment 5*) will be administered. Upon participant arrival at the lab, vital signs will be taken and documented at the beginning of the first stimulation session of the day. An EEG will then be administered, with ECG data also being collected at this time. The EEG recording will include resting state data along with an auditory task, and the EEG Questionnaire will be administered. The participant will receive 40-minutes of sham or 10 Hz tACS (as per the initial randomization) while sitting quietly with their eyes open. The *Reefscape* video will be played during the stimulation session. Each stimulation session will be followed by the stimulation adverse effects questionnaire. The BACS (*Attachment 6*) data collection assessments will be administered at the end of this session. If the participant opted to complete the clinical assessments in person, the AHRS (*Attachment 3*) and the PANSS (*Attachment 5*) will be administered at the end of this session. After the assessments are completed, the participant will then be paid at the completion of the session, and the first maintenance session will be scheduled for the second week after their last day of stimulation (one gap week in between).

---

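### Participants removed by rule are not asked for the week 8 AHRS, so primary t9 scores go uncollected on post-randomisation grounds

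*Combined protocol and SAP*

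**What the plan says.** Section 5.4.1 opens with "A study participant will be discontinued from further participation if". The grounds it lists include "The participant has missed 2 consecutive stimulation sessions during the initial week of stimulation", more than two non-consecutive misses over the study, and, for the second stage, "The participant has missed 2 consecutive weeks of stimulation during the maintenance sessions". They also include an adverse event or other condition that makes staying in contrary to the participant's interest, and "The participant meets any exclusion criteria (either newly developed or not previously recognized". Section 5.3 repeats the attendance part: "Participants will no longer be eligible to continue the study if they miss 2 consecutive stimulation sessions during the initial week of stimulation".

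Section 5.4.2 then says what is collected afterwards. For all exits: "In any case, every effort will be made to undertake protocol-specified safety follow-up procedures". For one type of exit it goes further: "If voluntary withdrawal occurs, the participant will be asked to continue scheduled evaluations and complete an end-of-study evaluation". The safety assessments described in 8.1 are vital signs, PANSS, C-SSRS and the stimulation adverse effects questionnaire. The AHRS is not among them.

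After randomisation, sections 7.1 and 7.4 place the AHRS on days 1 and 5 of stimulation and at each weekly maintenance session. Screening visits 2 to 4 are held by webex, and day 5 allows a remote rating: "If they prefer the phone/webex, the participant will be contacted before coming into the lab". That option is written for a participant who is still attending.

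Sections 4.1.1 and 10.2 base the primary analysis on the AHRS at t1 (day 5) and t9 (week 8). Section 10.2 also excludes the whole data set of anyone who stops before completing the sessions.

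**The concern.** Missed sessions, adverse events and newly met exclusion criteria all arise after randomisation, and each may depend on the assigned regimen or on clinical course. One example is a participant who starts a daily benzodiazepine: that meets an exclusion criterion in 5.2 and so triggers removal under 5.4.1. If the outcome is sought from those who choose to leave but not from those made to leave, the missing primary scores are tied to post-randomisation events. An analysis rule can be amended later, but a rating never taken cannot be recovered.

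The attendance rule also takes no account of which visits carry the endpoint. A participant who misses only week 8 stays in the trial but has no scheduled t9 rating. One who misses weeks 3 and 4 is removed, although a week 8 rating might have been obtained.

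**Working it through.** **The plan's own figure.** Section 10.3 gives 90% power [50%, 99%] for a period-1 difference of 1.18 AHRS units, using t1 and t9, N = 40 and size 0.025. Inputs from 10.3: conditional variance 5.53 (95% CI 2.96 to 13.72) and correlation 0.90.

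- Var(μS − μA) = 5.53 × (2/20) × (1 − 0.81) = 0.105, SE 0.324.
- Noncentrality = 1.18² / 0.105 = 13.25.
- Noncentral F(1, 37) gives 89.9%. Variances 13.72 and 2.96 give about 50% and 99.5%. The figure reproduces.

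**Precision if scores are lost.** Dropping 10 participants entirely, with 30 completers split 8/7/7/8, gives 77.6%. Keeping t1 for all 40 and losing t9 in 10 gives 80% to 81%, depending on the degrees of freedom. These figures concern precision only and say nothing about selective loss.

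**How many the attendance rules remove.** The documents give no miss rate, so p is an assumption shown over a range. Day 1 is taken as attended, because 10.4.1 links the participant to a randomisation code that day. The other 12 sessions (days 2 to 5, weeks 1 to 8) are each missed independently with probability p, and q = 1 − p. Removal means two consecutive misses within the stimulation week, two consecutive within maintenance, or more than two in total.

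- Retained patterns: no miss (1), one miss (12), or two misses that are not consecutive within a block (66 − 3 − 7 = 56).
- P(removed) = 1 − (q¹² + 12pq¹¹ + 56p²q¹⁰). At p = 0.10: 1 − (0.2824 + 0.3766 + 0.1953) = 0.1457.
- P(removed in week 1) = 1 − (q⁴ + 4pq³ + 3p²q²). At p = 0.10: 1 − (0.6561 + 0.2916 + 0.0243) = 0.028.
- P(retained, but day 5 or week 8 missed) = 2pq¹¹ + 19p²q¹⁰. At p = 0.10: 0.0628 + 0.0662 = 0.129.

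| Miss rate per session | Removed | Of 40 | Removed in week 1 | Retained, day 5 or week 8 missed |
|---|---|---|---|---|
| 5% | 3.5% | 1.4 | 0.7% | 8.5% |
| 10% | 14.6% | 5.8 | 2.8% | 12.9% |
| 15% | 30.8% | 12.3 | 6.1% | 13.4% |

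If day 1 could also be missed, removal would be 4.0%, 16.8% and 35.0%. At 10%, 8.5 of the 14.6 percentage points removed (58%) are attendance patterns that include both day 5 and week 8. In those the rule, rather than absence at the endpoint visit, costs the score. Misses that cluster within participants would change all these figures. Removals for adverse events or new exclusion criteria come on top and cannot be estimated from the documents.

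**The case against.** **The plan does not forbid later ratings.** Voluntary withdrawal stands in 5.4.1 under the same opening words as the other grounds, yet 5.4.2 still asks those participants to continue evaluations. So being discontinued does not in itself rule out an AHRS. This stands: the defect is that the plan is silent about the other exits, and one sentence would cure it.

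**Most of those removed already have t1.** This also stands. Only week-1 removals can lose t1, so the uncollected score is mainly t9. A reader might infer that both primary scores are lost wholesale, and the visit schedule does not support that.

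**The last column of the table overstates lost scores.** This stands as well. Day 5 can be rated by phone before the visit, and the documents do not say whether a missed visit may be rescheduled. Those percentages are upper bounds.

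**A figure for the bias.** A reader might take the 30-of-40 scenario in 10.3 as a 25% removal rate, multiply it by an assumed difference between regimens in how lost and retained participants fare, and compare the product with 1.18. The documents support none of these steps. The 30 allows for incomplete data of any kind and is not a rule-removal rate. No such difference between regimens is given. And 1.18 is the period-1 contrast, whereas t9 carries a different one.

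**Collection alone changes nothing in the planned analysis.** Correct, because 10.2 would still exclude anyone who stops early. Both sections need amending.

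**Conclusion.** The gap is real, though narrower than a reader might assume. No section provides for a t9 AHRS, or a t1 AHRS for those removed before day 5, from a participant removed by rule. Voluntary withdrawers are asked for theirs, and no reason is given for the difference. Under the stated assumptions the attendance rules remove between 1.4 and 12.3 of 40 participants at miss rates of 5% to 15%. Up to a further 8.5% to 13.4% stay in but miss the day 5 or week 8 session. The loss rests on post-randomisation events that may relate to treatment or worsening. Whether it differs between regimens, and in which direction, cannot be read from the documents. It is worth correcting because the scores cannot be recovered later and the means of collecting them are already in the protocol.

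**What to change.** Leave the grounds for stopping and their consequences in 5.3, 5.4.1 and 8.4.1 to the sponsor. In 5.4.2, extend the existing sentence along these lines:

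> *Unless consent is withdrawn or the investigator judges further contact not to be in the participant's interest, any participant who is discontinued for any reason, or who misses the day 5 or week 8 session, will be asked to complete the AHRS by phone/webex on the scheduled t1 and t9 dates; the reason and date of stopping will be recorded.*

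The sponsor should reconcile this wording with the opening of 5.4.1 and with 8.4.1, which ends participation at once in pregnancy.

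In 10.2, replace the completers-only rule so that every randomised participant with an available t1 or t9 AHRS enters the mixed model as randomised.

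The cost is an amendment of a few sentences and at most two remote interviews per affected participant, done by existing raters. The downside is that some t1 and t9 scores will be taken remotely or off stimulation. Recording the reason and date of stopping lets these be identified in the analysis.

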## 5.5 PREMATURE TERMINATION OR SUSPENSION OF STUDY

This study may be prematurely terminated if, in the opinion of the investigator, there is sufficient reasonable cause. Circumstances that may warrant termination include, but are not limited to:

- Discovery of unexpected, significant, or unacceptable risk to participants.
- Insufficient adherence to protocol requirements.
- Data that are not sufficiently complete and/or evaluable.
- Plans to modify, suspend or discontinue the development of the study device.

The IRB will be informed promptly and provided the reason(s) for the termination or suspension by the sponsor or by the investigator/institution, as specified by the applicable regulatory requirement(s).

## 6 STUDY INVESTIGATIONAL PRODUCT

### 6.1 STUDY PRODUCT DESCRIPTION

#### 6.1.1 DEVICE DESCRIPTION

Participants will be stimulated with the commercial, CE-certified Neuroconn Plus stimulator. The use of this device in this study has previously received a NSR designation on initial review by the full UNC IRB. The NeuroConn device description is as follows:

The DC-STIMULATOR is a CE-certified medical device for conducting non-invasive transcranial direct-current stimulation (TDCS) in humans. DC stimulation is used in clinical practice and in the research of stroke, epilepsy, migraine, tinnitus, depression, multiple sclerosis, dementia and chronic headache. The DC-STIMULATOR is a micro-processor-controlled constant current source. It meets the highest safety standards thanks to (hardware- and software-based) multistage monitoring of the current path. By continuously monitoring electrode impedance it can detect insufficient contact with the skin and automatically terminate stimulation, maximizing patient safety.

The device's alphanumeric display and the 4 touch keys allow various stimulation modes to be selected and stimulation parameters such as current strength, duration, fade-in and fade-out to be set.

DC-STIMULATOR features:

- 1 channel (anodal and cathodal stimulation possible)
- Adjustable current up to 5,000  $\mu$ A \*
- Adjustable application time up to 30 minutes \*
- 2 standard modes - single (continuous stimulation) and - pulse (cyclical stimulation activation/deactivation) with fade in and fade out
- Customer-specific programs possible (optional)
- "Study mode" for blind processing of genuine and 'pseudo' stimulation (optional)
- External trigger input (optional)

#### 6.1.2 OPERATION

- A. The desired current value is scaled to a register value and stored in the function generator.
- B. The value in the register determines the percent of full scale output current, generated by the function generator.
- C. The generated current waveform from the function generator is driven through a specified resistance. The resulting voltage drop is amplified by an instrumentation amplifier.
- D. The voltage waveform from the output of the instrumentation amplifier is applied to a voltage controlled current source.

*Current Sensor Circuit*

A  $33.2\ \Omega$  sense resistor is placed in series with the stimulation electrodes on the high side. Since high-side current sensing is used, any short circuit of the electrode terminals to ground will be detected. The stimulation current flows through this resistor and generates a voltage. The voltage across this resistor is sensed and amplified by the AD628 difference amplifier. The gain of the difference amplifier is set to 9.9039. The current sensor voltage is then shifted before it is read by the microprocessor and the hardware overcurrent safety feature.

#### *Voltage Sensor Circuit*

The differential voltage across the electrodes is measured so that the impedance can be calculated. The voltage is measured by buffering the positive electrode and negative electrode each with a unity gain op-amp circuit. The voltage sensor output is then shifted before it is read by the microprocessor using the same level shifting circuit described in the current sensor section.

[figure not shown]
---

#### 6.1.3 SAFETY PRECAUTIONS

The device is equipped with 4 different stages of safety protection, all of which protect the stimulant from high currents. The stages are as follows:

1. Automatic software current cutoff. The output of the current sensor described above is read by a microprocessor, which compares the reading to a value of  $+/3\text{mA}$  peak. If the current exceeds these limits, stimulation is stopped, a relay in series with the electrode is opened, and the power supply used for stimulation is turned off. The user is then given the option to investigate the issue, and cancel or resume the test. Since high-side current sensing is used (described above), any short circuit of the electrode terminals to ground will be detected.
2. Automatic hardware current cutoff. The output of the current sensor is fed into a pair of comparators which detect if the current exceeds  $+/4.5\text{mA}$ . If so, the fault is latched such that the relay in series with the electrodes is opened. Additionally, the microprocessor is notified of this instance through an interrupt. Upon this interrupt, the microprocessor immediately stops stimulation and the power supply used for stimulation is turned off.

Figure 1: Example of successful hardware cutoff function

3. Permanent hardware current cutoff. A 5mA fast-acting fuse is in series with the electrode connector. If the above two over-current detection methods fail, the fuse will blow, and the stimulant will no longer be electrically connected to the device.

4. Power supply fuse. Finally, if for any other reason the entire device draws too much current, the main power supply fuse is blown. This fuse is sized with a cutoff of 200% of steady-state operating current.

### **Digitizing scanner**

We will be using a GeoScan digitizing scanner to scan individual locations of scalp EEG electrodes. The GeoScan handheld digitizing scanner integrates into OEM neurodiagnostic equipment to measure, identify, and map electrode positions (via attached markers). This is based on optical 3D measurement technology that scans up to 256 markers in less than 2 minutes to accuracy within 0.5 mm and repeatability of 0.1 mm. Real-time compensation for data variability ensures only actual markers are measured for mapping and registration purposes.

GeoScan Digitizing Scanner

- Features

#### **Scanner Specifications**

Dimensions (LxWxH) 155 mm x 75 mm x 300 mm

Weight 860 g

Power Requirements 100-250 V AC ~50/60 Hz, 1 A

#### **Sensor Specifications**

Measurement Volume 883 mm x 840 mm x 928 mm

Update Frequency 20, 30, 60 Hz

Scan Rate 256 markers < 2 minutes

Accuracy Within 0.5 mm RMS

Stand-off 105 mm from the scanner

[figure not shown]
Depth of View 778 mm

Near field width 276 mm

Far field width 840 mm

Safety IEC 60601-1 3rd Edition

- Operation

		
1. Attach each electrode (with prefixed marker) to the scalp or cap.	2. Scan the head with the device to localize each marker's position. This localization process creates a digital point cloud (3D model) and rigid body of marker coordinates.	3. Probe anatomical features to establish fiducial (reference) points with respect to the rigid body, such as the nasion, inion, and preauricular points of the subject's head.

## 7 STUDY PROCEDURES/EVALUATIONS

### 7.1 STUDY SPECIFIC PROCEDURES

During the initial session, researchers will collect demographics. Participant demographics include medical history and medication history. This information is used to confirm inclusion criteria and that no current alcohol and drug abuses or disorder exist.

Several clinical evaluations will be used throughout this study. These assessments are listed below and can be found in the attached documents.

- i. The Structured Clinical Interview for DSM-IV Axis I Disorders (SCID-I) is a semi-structured interview used to diagnosis major Axis I disorders. For this study, the SCID-I (First et al. 2004) will be administered at baseline in order to confirm a diagnosis of Schizophrenia or Schizoaffective Disorder.
- ii. The Columbia Suicide Severity Rating Scale (C-SSRS) is a semi-structured interview designed to assess suicidality. The assessment will be administered at baseline, the first day of stimulation, the fourth maintenance stimulation session, and the final maintenance stimulation session.
- iii. The Auditory Hallucination Rating Scale (AHSRS) is a structured interview, designed to assess different aspects of patient's auditory hallucinations. This assessment has 11 items and is rated on a scale of 0 – 4 based on the responses given by the patient. The AHSRS will be administered at the baseline visit, each screening session, the first day of stimulation, the last day of stimulation, and at each of the maintenance stimulation sessions.
- iv. The Positive and Negative Syndrome Scale (PANSS) is a structured interview used to assess the symptom severity of patients diagnosed with schizophrenia. The PANSS (Kay et al. 1987) focuses on the positive and negative syndromes and their general severity. This scale will be administered at the

first day of stimulation, the last day of stimulation and at the final maintenance stimulation session (week 8).

v. The Brief Assessment of Cognition in Schizophrenia (BACS) will be administered at the first day of stimulation, the last day of stimulation and at the final maintenance stimulation session (week 8) in order to monitor changes in participant cognition. This validated assessment (Keefe et al. 2004, Keefe et al. 2006) contains 6 tests that focus on verbal memory and learning, working memory, motor functioning, attention/processing speed, verbal fluency and reasoning and problem solving.

